Persistence ^c	A urine culture taken at the EOT visit ^d grows a uropathogen (at $\geq 10^4$ CFU/mL) found at study entry.
Super infection	An infection-site culture grows a uropathogen (at $\geq 10^5$ CFU/mL) other than a baseline pathogen during the course of IV study therapy OR emergence during IV study therapy of a new pathogen at a distant (non-urine), sterile site along with worsening signs and symptoms of infection.
Indeterminate	
 a) Follow-up urine culture is not available at the EOT visit due to subject death or withdrawal from study; OR b) Microbiological data are incomplete; OR c) Assessment not possible due to protocol violation; OR d) Any other circumstance which makes it impossible to define the microbiological response

^a A microbiological response rating will be determined separately for each pathogen isolated at baseline. If a new/emergent pathogen is identified at this visit which was not identified at baseline, the microbiological response rating will be considered “super infection” for any new/emergent pathogen isolated after initiation of IV study therapy.

^b A favorable overall microbiological response at EOT requires “eradication” of all baseline pathogens.

^c If a subject is discontinued from IV study therapy due to clinical failure (i.e., unfavorable clinical response), but persistence of the admission pathogen is not confirmed by culture results or no culture is obtained at the time of clinical failure, the admission pathogen will be presumed to have persisted.

^d If a culture is not available at EOT, an assessment at this visit can be made from the last available urine culture which was collected after at least 48 hours of IV study therapy.

Table 7 Definitions of the By-Pathogen Microbiological Response for cUTI at the TOC Visit

Microbiological Response ^{a,b}	Response Definition
Sustained eradication ^c	A urine culture taken at the TOC visit still shows eradication of the uropathogen (e.g., $\geq 10^5$ CFU/mL is reduced to $< 10^4$ CFU/mL) found at study entry.
Persistence	A urine culture taken at the TOC visit grows a uropathogen (at $\geq 10^4$ CFU/mL) found at study entry.
New Infection	A uropathogen, other than a microorganism found at baseline is present in the urine (at a level $\geq 10^5$ CFU/mL) any time after IV study therapy is finished; OR A pathogen is isolated from a distant (non-urine), sterile after IV study therapy has been completed.

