Recurrence	A urine grows a uropathogen (at a level $\geq 10^5$ CFU/mL) taken any time after documented eradication.
Indeterminate	a) Follow-up urine culture is not available at the EFU visit due to subject death or withdrawal from study; OR b) Microbiological data are incomplete; OR c) Assessment not possible due to protocol violation; OR d) Any other circumstance which makes it impossible to define the microbiological response

^a A microbiological response rating will be determined separately for each pathogen isolated at baseline. If a new/emergent pathogen is identified at this visit which was not identified at baseline, the microbiological response rating will be considered a “new infection” for any new/emergent pathogen isolated after initiation of IV study therapy.

^b A favorable overall microbiological response at TOC visit requires “sustained eradication” of all baseline pathogens.

^c A microbiological response of “sustained eradication” at TOC is used when the microbiological response assessment at EOT visit is also “eradication”.

4.2.3.2.1.2.3 Composite Clinical and Microbiological Response (only for cUTI)

Composite clinical and microbiological response at each timepoint will be determined by Sponsor based on the clinical response evaluated by investigator and overall microbiological response (per subject) determined by Sponsor. Only the subject who have favorable outcomes for both of the clinical response and overall microbiological response will be determined as ‘favorable’ for composite clinical and microbiological response at each timepoint.

Details regarding determination of the category of clinical response and overall microbiological response outcome (“favorable” or “unfavorable”) in support of relevant study endpoints are provided in the tables describing clinical response or microbiological response as well as in Section 8.4.2.

4.2.3.2.1.3 Efficacy Criteria for sepsis

4.2.3.2.1.3.1 Clinical Response

Clinical response for sepsis will be assessed for subjects meets the criteria of sepsis (refer to section 5.1.2, inclusion criteria #2) based on evaluation by the investigator at the EOT and TOC visits. Based on comparison to baseline clinical signs and symptoms of sepsis, the investigator will determine the clinical response rating (and record the response on the appropriate eCRF) at each visit as described in [Table 8](#) (for EOT visit) and [Table 9](#) (For TOC visit).

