8.6.2 Statistical Methods for Efficacy Analyses

Missing values

In the analyses using the ME population, any subject with missing or indeterminate assessments for a specific endpoint (clinical or microbiological response) at any particular visit will be excluded from the assessment of that response at that time point. Exceptions follow:

1. (cIAI only) Subjects with a missing culture in the setting of a favorable clinical response: In such subjects, even in the setting of a missing culture at a particular time point, a favorable microbiological response will be presumed from the clinical response (i.e., "presumptive eradication").
2. Subjects discontinuing IV study therapy due to lack of efficacy (i.e., withdrawals with subsequent non-study antibiotic therapy, subjects requiring therapy beyond 14 days), including death due to index infection:
 - These subjects will be considered to be "failures" with respect to clinical response at the time of discontinuation and all subsequent time points post discontinuation, irrespective of whether the clinical response is listed as "indeterminate".
 - These subjects will be considered to have presumed persistence with respect to microbiological response at the time of discontinuation and all subsequent time points post discontinuation, irrespective of whether the microbiological response is listed as "indeterminate."

In the analyses using the MITT population, missing or indeterminate clinical or microbiological responses will be considered failure.

Proportions of subjects with favorable clinical/microbiological responses

A 95% CI based on the method of Agresti and Coull will be provided for the proportion of subjects with cIAI in the ME population achieving favorable clinical response at the EOT visit. The same analysis will be performed for the proportion of subjects with cUTI in the ME population achieving favorable microbiological response at the EOT visit. The same measures at the TOC visit will also be analyzed in the same manner. Supportive analysis using the MITT population will also be performed.

Table 18 summarizes key efficacy analyses.

Table 18 Analysis Strategy for Key Efficacy Variables

Endpoint/Variable (Description, Time Point)	Primary vs. supportive approach [†]	Statistical Method	Analysis Population	Missing Data Approach
Primary objectives				
Proportion of subjects with cIAI achieving favorable clinical response at the EOT visit	P	Agresti and Coull	ME	Data as observed [‡]

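### For cUTI subjects with no usable EOT rating, Table 7 keeps a positive TOC culture as a failure but leaves a negative one unrated, so inclusion in the TOC ME analysis depends on the TOC result

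*Combined protocol and SAP*

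**What the plan says.** The cUTI microbiological response at TOC is a secondary endpoint (Section 3.2). Four parts of the plan govern it.

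- **Favorable rating.** Table 7 footnote b begins: "A favorable overall microbiological response at TOC visit requires". The requirement is sustained eradication of every baseline pathogen. Table 17 lists no other favorable TOC rating for cUTI, since presumptive eradication is marked as cIAI only. Footnote c says that sustained eradication "at TOC is used when the microbiological response assessment at EOT visit is also" eradication, and the row itself asks that the culture still show it.
- **Unfavorable ratings.** The Persistence row reads "A urine culture taken at the TOC visit grows a uropathogen", at 10^4 CFU/mL or more and found at entry, with no condition on EOT. Recurrence applies to a culture "taken any time after documented eradication".
- **Residual rating.** Indeterminate covers incomplete microbiological data and "Any other circumstance which makes it impossible to define the microbiological response".
- **Missing data (Section 8.6.2).** In the ME analysis a subject with a missing or indeterminate assessment "will be excluded from the assessment of that response at that time point". In MITT, "missing or indeterminate clinical or microbiological responses will be considered failure".

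Table 6 footnote d allows the EOT rating to come from the last urine culture taken after at least 48 hours of IV therapy when the EOT culture is not available. The flow chart schedules cUTI urine cultures at screening, Day 3, EOT and TOC.

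**The concern.** Section 8.6.2 handles missing data visit by visit: a gap at EOT should cost the subject the EOT analysis and nothing else. Footnote c carries the EOT gap forward to TOC, but only for subjects whose TOC culture is negative. Within the group that has no EOT rating, observed TOC successes leave the ME denominator and observed TOC failures stay. This is selection on the outcome being estimated. In MITT the approach that Table 18 labels missing equals failure is applied to a TOC culture that was taken and was negative. The exploratory cUTI composite at TOC inherits the same rating.

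**Working it through.** **Step 1: the plan's own figure.** Agresti-Coull with z = 1.96: n~ = n + z², p~ = (x + z²/2)/n~, limits p~ ± z·sqrt(p~(1 − p~)/n~). For 26 of 28, n~ = 31.84, p~ = 0.877 and the half-width is 0.114, giving 92.9% (76.3%, 99.1%). This matches Section 8.9, and the other rows of Table 19 also reproduce. No stated figure is in dispute; the point concerns a rating rule.

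**Step 2: trace two records.** Both are cUTI subjects in the ME population with no usable EOT rating after the footnote d fallback.

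| TOC urine culture | Table 7 rating | ME at TOC | MITT at TOC |
|---|---|---|---|
| Baseline uropathogen below 10^4 CFU/mL | Not sustained eradication (EOT was not eradication), not Persistence, not Recurrence; hence Indeterminate | Excluded | Failure |
| Baseline uropathogen at 10^4 CFU/mL or more | Persistence | Failure | Failure |

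Neither exception in Section 8.6.2 rescues the first record. The one that presumes eradication is limited to "cIAI only) Subjects with a missing culture in the setting of a favorable clinical response", and the lack-of-efficacy exception only assigns unfavorable ratings. The ME exclusions listed in Section 8.5.2 do not include a missing EOT culture, so nothing removes the second record.

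**Step 3: size in ME.** The documents give neither the number m of 28 ME subjects without an EOT rating nor the true TOC rate p. I assume m = 1 to 2 and p = 60% to 90%. I also assume that a missing EOT rating is unrelated to the TOC result, that all 28 have a TOC culture, and that every other subject clear at TOC was rated eradication at EOT. The ratio of expected counts is

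estimate = (28 − m)p / [(28 − m) + m(1 − p)].

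| m | p = 60% | p = 80% | p = 90% |
|---|---|---|---|
| 1 | 16.2/27.4 = 59.1% (−0.9) | 21.6/27.2 = 79.4% (−0.6) | 24.3/27.1 = 89.7% (−0.3) |
| 2 | 15.6/26.8 = 58.2% (−1.8) | 20.8/26.4 = 78.8% (−1.2) | 23.4/26.2 = 89.3% (−0.7) |

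In counts, 22 clear of 28 is 78.6% (60.1%, 90.1%). Dropping two clear subjects gives 20/26 = 76.9% (57.6%, 89.3%). The shift of 1.7 points compares with an interval half-width of 15.0 points.

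**Step 4: size in MITT.** With 40 enrolled in the cohort, each affected subject with a negative TOC culture costs 1/40 = 2.5 points. The expected loss is m·p/40: at p = 80%, 2.0 points for m = 1 and 4.0 points for m = 2.

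**Step 5: the opposing group.** By the same reading, a subject with Persistence at EOT and a negative TOC culture also fits only Indeterminate, unless the lack-of-efficacy exception applies. If that subject should count as unfavorable, dropping one moves 22/28 (78.6%) to 22/27 (81.5%), or +2.9 points. The phase II cUTI study had 64/67 favorable at the end of IV therapy on the 250 mg dose (Section 4.1.2), so 3/67 × 28 = about 1.3 unfavorable EOT ratings per 28. How many of those would clear by TOC is not known.

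**The case against.** **Footnote d removes most of the group.** It does reduce the number, and this is why I use 1 to 2 of 28 and not more. It need not reduce it to zero. Day 3 is the only scheduled culture between baseline and EOT, and it can fall before 48 hours: a first dose at 18:00 on Day 1 and a sample at 09:00 on Day 3 are 39 hours apart. An EOT rating can also be Indeterminate because of incomplete data or a protocol violation.

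**Footnote c does not say 'only when'.** This is fair as to wording. But with no restrictive force the footnote would do nothing, and 'still' in the row points the same way. If the looser reading is intended, the text should say so, because the two readings give different ratings.

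**The pre-lock memo on ME composition (Section 8.5.2) can settle it.** It could, but the plan gives no rule for it to apply, and the trial is open-label.

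**Requiring eradication at both visits is a legitimate definition of sustained eradication.** It is. The defect is that the rule is not matched by one for positive cultures when EOT is unknown.

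**Little is at stake.** This also stands in part: the endpoint is secondary, the trial is single-arm estimation with no hypothesis test, and MITT is a supportive analysis that is conservative by design.

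**Conclusion.** The asymmetry is real on the text and is worth correcting, but it is small. Under the assumptions in Step 3 the ME estimate falls by about 0.3 to 1.8 points, against interval half-widths of roughly 11 to 15 points (26/28 and 22/28). The supportive MITT rate loses 2.5 points per affected subject with a negative TOC culture, per 40 enrolled.

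A reader might infer that the secondary cUTI endpoint as a whole is biased downward. The documents do not support that. The downward effect is shown only within the group with no EOT rating; the treatment of EOT persistence followed by a negative TOC culture can push the estimate up by more, and the size of neither group is given.

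A reader might also infer an equal problem in cIAI, because Table 5 footnote c has the same wording: after presumptive eradication at EOT, a culture-negative TOC specimen fits neither favorable rating. That is a matter of consistency only. The cIAI microbiological endpoint is exploratory, its methods are deferred to the supplemental SAP, and follow-up specimens are not required where collection is not medically acceptable, so such records should be uncommon.

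**What to change.** 1. Reword Table 7 footnote c: when the EOT rating is missing or indeterminate after the footnote d fallback, rate TOC on the TOC culture in both directions. A negative culture (below 10^4 CFU/mL) is favorable; the baseline pathogen at 10^4 CFU/mL or more is persistence. Keep this subject to exception 2 of Section 8.6.2, and add the favorable rating to Table 17.
2. State one rating, other than Indeterminate, for EOT persistence followed by a negative TOC culture.
3. For consistency, apply the same wording to Table 5 footnote c, covering presumptive eradication at EOT followed by a negative TOC specimen.

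Calling both TOC results Indeterminate when EOT is unknown would also remove the asymmetry, but it would discard observed TOC data.

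The cost is protocol and SAP wording and one derivation line. No new samples are needed, because the TOC urine culture is already required for cUTI. The downside is that a few favorable TOC ratings would rest on one negative culture and not two; these can be flagged in the listing.

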4.2.3.3 Pharmacokinetic Endpoints

At the timepoints specified in the Trial Flow Chart (Section 6.0), whole blood samples will be collected for determination of plasma concentration of REL, imipenem, and CIL. These samples will support further evaluation of the PK profiles of these drugs by confirming that subjects achieve expected exposures, and will also aid in further assessment of the clinical relationship between REL plasma concentrations and efficacy against resistant isolates.

4.2.3.4 Planned Exploratory Biomarker Research

Planned Genetic Analysis

Understanding genetic determinants of drug response and the molecular basis of disease is an important endeavor during medical research. This research will evaluate whether genetic variation within a clinical trial population correlates with response to the treatment(s) under evaluation and/or disease. If genetic variation is found to predict efficacy or adverse events, the data might inform optimal use of therapies in the patient population. Knowledge of the molecular basis of disease contributes to the development of novel biomarkers and the identification of new drug targets. This research contributes to understanding molecular basis of disease and the genetic determinants of efficacy and safety associated with the treatments in this study.

4.2.3.5 Future Biomedical Research

The Sponsor will conduct Future Biomedical Research on DNA specimens consented for future biomedical research during this clinical trial.

Such research is for biomarker testing to address emergent questions not described elsewhere in the protocol (as part of the main trial) and will only be conducted on specimens from appropriately consented subjects. The objective of collecting/retaining specimens for Future Biomedical Research is to explore and identify biomarkers that inform the scientific understanding of diseases and/or their therapeutic treatments. The overarching goal is to use such information to develop safer, more effective drugs/vaccines, and/or to ensure that subjects receive the correct dose of the correct drug/vaccine at the correct time. The details of this Future Biomedical Research sub-trial are presented in Section 12.2 – Collection and Management of Specimens for Future Biomedical Research.

4.3 Benefit/Risk

Subjects enrolled in this trial are hospitalized subjects with infections requiring treatment with IV therapy. Subjects will receive treatment, in part, with an agent, IMI, recommended and commonly used for the treatment of such infections, and, in addition, subject can potentially benefit from treatment with the investigational agent REL.

Although potentially more frequent than standard of care, the study procedures described in Section 6.0 (Trial Flow Chart) are generally typical procedures performed for this hospitalized subject population. Additional burden may be incurred due to visits following release from the hospital. However, the procedures performed at these visits are generally not likely to lead to significant harm (e.g., blood draws, urine collection, physical exam, vital signs). These procedures are necessary to support a robust evaluation of the safety and efficacy of the investigational drug with potential to support treatment of subjects for whom no or limited alternative therapies are available.

Additional details regarding specific benefits and risks for subjects participating in this clinical trial may be found in the accompanying Investigators Brochure (IB) and Informed Consent documents.

5.0 METHODOLOGY

5.1 Entry Criteria

5.1.1 Diagnosis/Condition for Entry into the Trial

Male/Female Japanese subjects who are at least 18 years of age and have been diagnosed with complicated intra-abdominal infection (cIAI) or complicated urinary tract infection (cUTI) will be enrolled in this trial.

5.1.2 Subject Inclusion Criteria

In order to be eligible for participation in this trial, the subject must:

1. be \geq 18 years of age on the day of signing informed consent.
2. require hospitalization and treatment with IV antibiotic therapy for complicated intra-abdominal infection (cIAI) or complicated urinary tract infection (cUTI)

NOTE: Subjects have to meet the following diagnostic criteria, including relevant clinical and microbiological evidence for each infection type.

Complicated Intra-Abdominal Infection (cIAI)

A. Definition

Intra-abdominal infection (IAI) is broadly defined as peritoneal inflammation in response to microorganisms, resulting in purulence in the peritoneal cavity. IAI are classified as uncomplicated or complicated based on the extent of infection. Complicated IAI (cIAI) extends beyond the hollow viscus of origin into the peritoneal space and is associated with either abscess formation or peritonitis.

B. Diagnostic Guidelines

Subject has clinical evidence on the basis of operative findings and is able to provide the specimen to confirm the microbiological findings at baseline. Procedures include open laparotomy, laparoscopy, and percutaneous drainage of intra-abdominal abscess. Postoperative (or intraoperative) enrollment of subjects is encouraged. If, however, preoperative data are available that strongly suggest an appropriate diagnosis for entry (e.g., intraperitoneal abscess or perforation on computed tomography [CT] scan), then these subjects may be enrolled preoperatively. For preoperative enrollment, subjects must have a surgical intervention performed within 24 hours of the initiation of IV study drug.

1. Clinical

A diagnosis of cIAI should include at least one of the following as evidence of intra-peritoneal infection (or strongly suggested with an appropriate diagnosis confirmed by CT scan):

- Intra-abdominal abscess, including splenic or liver abscess
- Appendicitis complication by perforation or abscess formation
- Diverticulitis complicated by perforation or abscess formation
- Cholecystitis with evidence of perforation or empyema
- Perforation of the large or small intestine with abscess or fecal contamination
- Gastric or duodenal ulcer perforation, only if operated on >24 hours after perforation
- Peritonitis due to perforated viscus, surgical intervention, or other focus of infection. Spontaneous bacterial peritonitis associated with cirrhosis and chronic ascites are not eligible.

AND

At least one of the following clinical signs and symptoms of infection should be present:

- Fever, defined as oral temperature greater than or equal to 38.0°C [or axillary temperature greater than or equal to 37.5°C];
- Hypothermia, defined as core body temperature less than or equal to 35°C;
- Abdominal pain or flank pain, or pain caused by cIAI that is referred to another anatomic area such as back or hip
- Nausea or vomiting
- Elevated white blood cells (WBC; >10,500/mm³)

2. Microbiological

Purulent material from intra-abdominal space is able to be obtained during a surgical operation or percutaneous drainage at baseline. Specimens from the surgical intervention must be sent for aerobic and anaerobic culture.

Complicated Urinary Tract Infection (cUTI)

A. Definition

A complicated urinary tract infection is an infection of one or more structures in the urinary system in the presence of a functional or anatomical abnormality of the urinary tract or in the presence of catheterization. Pyelonephritis, regardless of underlying abnormalities of the urinary tract, is a type of cUTI that affects one or both kidneys. UTIs are a clinical syndrome characterized by pyuria and a documented microbial pathogen on culture of urine or blood, accompanied by local and systemic signs and symptoms of infection.

B. Diagnostic Guidelines

For a diagnosis of cUTI, including pyelonephritis, supportive clinical and microbiological findings should be present.

1. Clinical

Subject has at least two of the following local or systemic signs and symptoms:

- Local signs and symptoms: Dysuria, urinary frequency, suprapubic or pelvic pain, urinary urgency, or flank pain or costovertebral angle (CVA) tenderness on physical examination
- Systemic signs and symptoms: Fever (defined as oral temperature greater than or equal to 38.0°C [or axillary temperature greater than or equal to 37.5°C], chills or rigors (accompanied by fever), nausea or vomiting

AND

Pyuria determined by a midstream clean-catch (MSCC) or catheterized (indwelling or straight catheter) urine specimen with ≥ 10 white blood cells (WBCs) per high-power field (hpf) on standard examination of urine sediment or ≥ 10 WBCs/mm³ in unspun urine.

NOTE: If pyuria cannot be determined by urinalysis in a clinically relevant timeframe, a urine dipstick may be employed as a rapid diagnostic aid. If urine dipstick is used, a positive test for leukocyte esterase is the preferred indicator for the presence of pyuria.

2. Anatomical

Subject has at least one of the following conditions associated with a risk for developing cUTI:

- Indwelling urinary catheter or other urinary bladder instrumentation
- Urinary retention (at least 100 mL of residual urine after voiding)
- Neurogenic bladder
- Obstructive uropathy (nephrolithiasis, fibrosis or prostatic hypertrophy)
- Azotemia

OR,

Subject has pyelonephritis and normal urinary tract anatomy.

3. Microbiological

Subject has a positive urine culture at baseline as defined below:

- $\geq 10^5$ CFU/mL of uropathogen either from a mid-stream clean catch (MSCC) or indwelling catheter urine specimen, OR
- $\geq 10^4$ CFU/mL of uropathogen either from a MSCC or indwelling catheter urine specimen if blood culture is also positive

NOTE: For subjects with an indwelling catheter, samples should be collected following the placement of a new catheter. If the placement of a new catheter is contraindicated or is not feasible, specimens should be collected using aseptic techniques with the urine obtained through a properly disinfected collection port. Urine samples should never be obtained from a collection bag.

NOTE: If more than one pathogen is identified, each should be present at the colony counts noted above to be considered pathogens. In general, if more than 2 bacterial pathogens are identified in an admission urine culture at the predefined colony counts, the sample should be considered contaminated (unless one of the pathogens is also identified in a blood culture).

NOTE: A subject can be enrolled before the urine culture results are available if it is likely to be positive (based on clinical findings and urinalysis).

Sepsis secondary to cIAI or cUTI

The investigator should confirm if the subjects meet the following diagnosis for sepsis upon the study entry in addition to the one of diagnostic criteria for their primary infection. Subjects don't need to meet the criteria for sepsis to be enrolled into this study. However for subjects with sepsis, investigators should also follow the procedures for sepsis as determined in this protocol.

A. Definition

Sepsis is defined as a systemic inflammatory response syndrome induced by infection, with microbiologically documented.

B. Diagnostic Guidelines

Subjects should have clinical signs defined below and meet the following microbiologic criteria;

1. Clinical:

Temperature $\geq 38.0^{\circ}\text{C}$ or $< 36^{\circ}\text{C}$ [defined as oral temperature, and $\geq 37.5^{\circ}\text{C}$ or $< 35.5^{\circ}\text{C}$ as axillary temperature], with one of the following:

- WBC count $> 12,000$ or $< 4,000$, or with a differential count showing 10% band forms
- Tachycardia: Pulse rate > 100 bpm

- Tachypnea: Respiratory rate > 20 breaths/minute
- Hypotension: Systolic blood pressure < 90 mm Hg

2. Microbiologic criteria:

Subject has positive blood culture at baseline (within 24 hours of initiation IV study therapy)

3. have an infection known or thought to be, in the opinion of the investigator, caused by microorganisms susceptible to the IV study therapy.
4. whose baseline specimen from the primary infection-site for culture could be obtained during the following period;
 - For cIAI: intra-abdominal specimen obtained at operative procedure at screening period.

NOTE: For cIAI subject who enrolled pre-operatively enrollment, the specimen from the infection site obtained during the interventional procedure should be provided as baseline.

- For cUTI: Urine specimen within 48 hours prior to initiation of IV study drug.

5. agree to allow any bacterial isolates obtained from protocol-required specimens related to the current infection to be provided the Central Microbiology Reference Laboratory for study-related microbiological testing, long-term storage, and other future testing.
6. understand (or have a legal representative that understands) the study procedures, alternative treatments available, and risks involved with the study, and voluntarily agree to participate by giving written informed consent for the trial. The subject or legally acceptable representative may also provide consent for Future Biomedical Research. However, the subject may participate in the main trial without participating in Future Biomedical Research.
7. meet one of the following categories:
 - a) The subject is a male who is not of reproductive potential, defined as a male who has azoospermia (whether due to having had a vasectomy or due to an underlying medical condition).
 - b) The subject is a female who is not of reproductive potential, defined as a female who either: (1) is postmenopausal (defined as at least 12 months with no menses in women ≥ 45 years of age); (2) has had a hysterectomy and/or bilateral oophorectomy, bilateral salpingectomy, or bilateral tubal ligation/occlusion at least 6 weeks prior to screening; OR (3) has a congenital or acquired condition that prevents childbearing.

c) The subject is a female or a male who is of reproductive potential and agrees to avoid becoming pregnant or impregnating a partner from the time of consent through completion of the study by complying with one of the following: (1) practice abstinence from heterosexual activity OR (2) use (or have their partner use) acceptable contraception during heterosexual activity. Acceptable methods of contraception are:

Single method (one of the following is acceptable):

- non-hormonal intrauterine device (IUD)
- vasectomy of a female subject's male partner

Combination method (requires use of two of the following):

- diaphragm with spermicide
- contraceptive sponge (nulliparous women only)
- male condom or female condom (cannot be used together)
- hormonal contraceptive: oral contraceptive pill (estrogen/progestin pill or progestin-only pill)

